1.3.4 Statistical analyses

Student t-test will be used as significance test for differences in blood pressure between the treatment groups.

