7.1 Variables

7.1.1 Outcome variables

Measures of feasibility

The primary outcome measure will be the rate of participation in the study; measured as:

- 1) the proportion of patients eligible for the study out of all patients with stroke admitted to the Department of Neurology,
- 2) the proportion of patients accepting to participate in the study, and
- 3) the degree of adherence to the intervention (proportion of attendance in follow-up sessions)

Aside from participation we will evaluate the participants' satisfaction with the overall intervention and single parts of the intervention.

Variable	Measure	Type/scale	Source
Admissions	Number of patients admitted in the study period	Continuous	
Eligibility	Number of patients who would be candidates for participation	Continuous	
Recruitment	Number of participants recruited	Continuous	
Adherence	Number of participants completing the treatment Degree of participation	Continuous	
Satisfaction	Five level Likert Scale	Ordinal	

Secondary outcome

Measure of effect

The secondary outcome measure will be arterial blood pressure measured 12 weeks after the start of the intervention. The arterial blood pressure will be measured as a continuous variable in mmHg. The participant should be sitting still and resting for ten minutes before the measurement. To avoid extreme values the measurement will be repeated three times with a few minutes apart and the median value will be used for the statistical analysis.

This outcome measure was chosen because hypertension is the most significant risk factor for stroke and TIA (5) and because previous studies have found that it might be possible to lower the blood pressure through lifestyle interventions (8).

Tertiary outcomes

Tertiary outcomes after 12 weeks will include:

Variable	Measure	Type/scale	Source
Changes in behavior			
Smoking	Daily; weekly; Rarely; Former; Never smoked	Categorical	B
Physical activity	Questionnaire	Ordinal	B
Adherence to medication	Questionnaire	Continuous	B
Anthropometric measures			
Body weight	Measured (kg)	Continuous	C
Height	Measured (cm)	Continuous	C
Waist + hip circumference	Measured (cm)	Continuous	C
Patient reported outcomes			
Fatigue	Questionnaire		B
Self-rated health	Two item questionnaire	Categorical	B

Secondary outcomes after one year will include:

Variable	Measure	Type/scale	Source
New stroke/TIA	Event + days till event	Categorical/time	A
Cardiac admission	Event + days till event	Categorical/time	A

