7.1.2 Other variables

Baseline data

Before the participants are randomized following baseline data will be collected (*the brackets state the type of data*):

Variable	Measure	Type/scale	Source
Diagnosis	ICD-10; established through clinical exam/CAT scan	Categorical	A
Gender	Male/Female	Categorical	A
Birthdate		Date	A
Symptom onset		Date/time	A/B
Admission		Date/time	A
Living arrangement	Living alone; living with partner; care facility; other	Categorical	B
Performance status (prior)	WHO performance status	Ordinal	B
Self-rated health	Two item questionnaire	Ordinal	B
Alcohol consumption (/week)	Within/above recommended level (7/14 units/week)	Categorical	B
Smoking	Daily; weekly; Rarely; Former; Never smoked For current smokers the amount and type of tobacco is also recorded	Categorical	B
Physical activity		Ordinal	B
Comorbidities	Charlson's Comorbidity Index: Aggregated scale based on weighted scores of presence or non-presence different diseases Individual diseases or groups will be coded as Y/N and the CCI will be calculated from these	Ordinal	A/B
Body weight	Measured (kg)	Continuous	C
Height	Measured (cm)	Continuous	C
Waist + hip circumference	Measured (cm)	Continuous	C
Stroke severity	Scandinavian Stroke Scale; Sub-scores: Consciousness, eye palsy, arm palsy, hand palsy, leg palsy, orientation, speech (dysphasia), facial palsy, gait	Ordinal	C
Vital signs	Early Warning Score; Sub-scores: Respiration rate, oxygen saturation, heart rate, temperature, systolic/diastolic blood pressure, consciousness	Ordinal	C
Cardiac rhythm	ECG: Normal; arterial fibrillation; other arrhythmia	Categorical	C
Blood glucose	S-glucose at admission; HbA1c	Continuous	C
Blood lipids	Total cholesterol, LDL, VLDL, HDL, triglycerides	Continuous	C

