8.1 Sample size calculations

The study in the current form is a randomized feasibility study where the main objective is to test if the intervention and study design is feasible enough for a full size study randomized controlled trial. We will therefore only include 40 participants in this phase of the study.

A full size randomized controlled trial will no doubt require a larger sample size if we were to expect an effect to be found. In a meta-analysis of fairly similar interventional studies Lawrence et al. found that the weighted means of the systolic blood pressure were 132.5 (SD 18.3; n=682) mmHg in the intervention groups and 136.2 (SD 21.5; n=725) in the control groups, respectively, and with a mean difference of 4.21 mmHg (95%CI 2.18-6.24).

Using the estimates from Lawrence et al. we can estimate the sample size needed with the method for comparing two means as reported by Kirkwood & Stern ((12)p 420) with the following assumptions:

- An equal number of participants are allocated to the two groups
- The blood pressure values are approximately normally distributed
- An alpha of 5 percent (probability of Type I error) and a beta of 20 percent (probability of Type II error)

From this it is estimated that we will need a sample-size of 596 (298 in each group), not adjusting for losses to follow-up.

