8.3 Statistical analysis

Hypothesis testing for the secondary outcome (systolic blood pressure) will be done as intention-to-treat (including all participants allocated) using a paired t-test comparing baseline systolic blood pressure with systolic blood pressure measured after 12 weeks. Results will be reported as mean difference of changes with 95 percent confidence intervals.

Tertiary outcome measures will be analyzed as intention-to-treat using unpaired student t-test for continuous variables and either chi-squared test or fisher's exact test for categorical variables. Treatment allocation will be blinded to the investigator.

Statistical analyses will be done in R 3.3.1/R Studio 0.99. A significance level of 5 percent will be considered statistically significant.

9 Validity and bias

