9.3 Confounding variables

In theory the random allocation of treatment should eliminate the effect of other confounders, as they would be equally distributed in the two groups. But given the limited sample-size we cannot be certain that this will be the case. One strategy to avoid this could be to stratify the randomization be a likely confounder (e.g. hypertension or smoking). But at this point we are not sure which confounder would be the best to stratify by and this will therefore be part of the feasibility evaluation.

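### Section 8.3 reports the blood pressure effect as a difference in change from baseline; adjusting 12-week pressure for baseline would be more precise at almost no cost

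*Combined protocol and SAP*

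**What the plan says.** All references are to the combined protocol and SAP.

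- **Analysis (8.3).** Systolic pressure is tested "using a paired t-test comparing baseline systolic blood pressure with systolic blood pressure measured after 12 weeks". The next sentence fixes the reported quantity: "Results will be reported as mean difference of changes with 95 percent confidence intervals". No baseline covariate is named here or elsewhere.
- **Synopsis (1.3.4).** "Student t-test will be used as significance test for differences in blood pressure between the treatment groups".
- **Outcome (7.1.1).** "The secondary outcome measure will be arterial blood pressure measured 12 weeks after the start of the intervention". After a rest, "the measurement will be repeated three times with a few minutes apart and the median value will be used for the statistical analysis". This procedure is given for the outcome reading only.
- **Baseline (7.1.2).** Baseline data precede randomization. Systolic pressure appears only among the Early Warning Score items: "Respiration rate, oxygen saturation, heart rate, temperature, systolic/diastolic blood pressure, consciousness". Section 6.1 has patients approached in hospital, generally in the opening days of the stay.
- **Chance imbalance (9.3).** On whether randomization will balance the arms: "But given the limited sample-size we cannot be certain that this will be the case". Only stratification is considered, and it is deferred.
- **Planning values (8.1).** The cited meta-analysis gives "132.5 (SD 18.3; n=682) mmHg in the intervention groups and 136.2 (SD 21.5; n=725) in the control groups", and a mean difference of 4.21 mmHg.

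**The concern.** A change score subtracts the whole baseline value from the 12-week value, however weakly the two are related. When the correlation is well below 1, that over-corrects. If the intervention arm happens to start higher, the change score shows a reduction that is partly regression to the mean. A linear model with baseline as a covariate estimates how much to subtract.

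The effect estimate and the variability of blood pressure are among the things this trial hands to the full-size trial (section 1.4). At 40 patients the interval is wide under any analysis, so avoidable width should go. The issue concerns the estimate and its interval. It is separate from the paired test, which compares times within patients rather than arms. Replacing that test with an unpaired test on the changes would leave this issue in place.

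**Working it through.** **The plan's own figure.** Section 8.1 gives 298 per group for a future trial comparing two means. With SD 18.3 in both arms, 4.21 mmHg, two-sided 5% and 80% power: 7.849 × 2 × 18.3² / 4.21² = 296.6, or 297.6 with the t-distribution, hence 298. It reproduces only if 18.3 is used for both arms; with 18.3 and 21.5 it is 354. The calculation uses the SD of attained pressure and no baseline information. The plan states no precision for the present trial.

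**Inputs.** N = 40 (8.1), taken as 20 per arm (assumed; no ratio is stated for this trial). SDs 18.3 and 21.5 (8.1), assumed to hold at both times. ρ is not in the documents, so a range is shown.

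**Formulas.**
- SE of an unadjusted difference at one time: √(18.3²/20 + 21.5²/20) = √39.857 = 6.31 mmHg; half-width 2.024 × 6.31 = 12.8.
- Change score: SE = 6.31 × √[2(1 − ρ)], 38 df (t = 2.024).
- Baseline-adjusted: SE = 6.31 × √[(1 − ρ²)(1 + 1/36)], 37 df (t = 2.026). The factor 1 + 1/(N − 4) is the cost of estimating the slope.

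| ρ | SE change | SE adjusted | Half-width change | Half-width adjusted | Variance ratio |
|---|---|---|---|---|---|
| 0.3 | 7.47 | 6.11 | 15.1 | 12.4 | 1.50 |
| 0.5 | 6.31 | 5.54 | 12.8 | 11.2 | 1.30 |
| 0.7 | 4.89 | 4.57 | 9.9 | 9.3 | 1.14 |
| 0.8 | 3.99 | 3.84 | 8.1 | 7.8 | 1.08 |
| 0.9 | 2.82 | 2.79 | 5.7 | 5.7 | 1.02 |

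Below ρ = 0.5 the change score is less precise than ignoring baseline. The adjusted analysis loses its advantage over the change score only when (1 + ρ)(37/36) exceeds 2, that is, above ρ ≈ 0.95.

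**Where the extra variance comes from.** 2(1 − ρ) = (1 − ρ²) + (1 − ρ)². The last term is the variance of the part of the baseline imbalance that enters the estimate. One SE of baseline imbalance is 6.31 mmHg, and the shift is (1 − ρ) × 6.31:

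| ρ | Shift for one-SE imbalance | P(absolute shift > 4.21) = 2[1 − Φ(4.21/shift)] |
|---|---|---|
| 0.3 | 4.4 mmHg | 34% |
| 0.5 | 3.2 mmHg | 18% |
| 0.7 | 1.9 mmHg | 3% |

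**Simulation check** (40,000 trials, SD 18.3, no true effect). The change-score estimate averaged about 0 overall. Given a baseline 5.8 mmHg higher in the intervention arm (one SE at that SD), it averaged −4.0, −2.9 and −1.7 mmHg at ρ = 0.3, 0.5 and 0.7. The adjusted estimate stayed within 0.05 of zero.

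**If the in-hospital baseline is more variable.** With a baseline SD 1.2 times the 12-week SD, the change-score factor is 1 + 1.44 − 2.4ρ, and the variance ratios become 1.84, 1.61 and 1.45 at ρ = 0.3, 0.5 and 0.7.

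**What ρ means for the full trial.** Scaling 296.6 per arm by 2(1 − ρ) or (1 − ρ²) gives, change score against adjusted, 416 against 270 at ρ = 0.3, 297 against 223 at 0.5, and 178 against 152 at 0.7. An unadjusted 12-week comparison needs 297 throughout.

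**The case against.** **The plan may not really commit to a change-score comparison.** The sentence on changes follows a paired test and could mean change within patients. Sections 1.3.4 and 7.1.1 point to a between-arm comparison of 12-week pressure, and reconciling section 8.3 with them would remove the change score. This stands as a comment on the text, but adjustment still helps. It beats an unadjusted 12-week comparison whenever (1 − ρ²)(37/36) < 1, that is, ρ above about 0.16. An unadjusted comparison also carries imbalance, in the opposite direction, by ρ times its size.

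**The driver is unknown.** Correct. No value of ρ is given, and at 0.8 or above with equal SDs the gain is small. A low ρ is plausible because baseline is taken during the hospital stay and the rest and three-reading procedure is stated only for 12 weeks. That is inference: the documents do not say that the baseline is the reading on arrival, or how it is taken.

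**Nothing hangs on this interval.** Half-widths of 12.8 or 11.2 mmHg are both inconclusive around 4.21 mmHg, and no decision rule uses them. This stands, and it limits the importance.

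**The variance for planning is not lost.** Section 1.4 already promises an estimate of blood pressure variance, and reporting changes does not prevent reporting the SD at 12 weeks. A reader might infer that section 8.3 yields only the SD of change, not the quantity used in section 8.1. The documents do not support that.

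**Conclusion.** The point holds as one of efficiency. Read as a between-arm contrast, the difference in change has 1.50, 1.30, 1.14 and 1.08 times the variance of a baseline-adjusted 12-week comparison at ρ = 0.3, 0.5, 0.7 and 0.8. This rests on 20 per arm, equal SDs at both times, and a ρ the documents do not supply.

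Three stronger readings are tempting and should not be drawn:

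- That the estimate is biased. It is not; the distortion is conditional on the imbalance that happens to occur.
- That imprecision and imbalance are two separate harms. They are one loss, already contained in the wider interval.
- That the whole imbalance becomes apparent effect. A raw baseline difference above 4.21 mmHg would arise in about half of such trials (2[1 − Φ(4.21/6.31)] = 0.50), but only the fraction (1 − ρ) reaches the estimate, hence the lower probabilities shown above.

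This is a free improvement of moderate importance. Sections 7.1.1 and 8.3 list systolic pressure as secondary in a 40-patient feasibility trial, although sections 1.3.2 and 7.5 call it primary.

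**What to change.** In section 8.3, when the paired test is corrected, make the reported result the adjusted mean difference in 12-week systolic pressure, from a linear model of 12-week pressure on arm and baseline pressure, with its 95% CI. If the log transform raised in section 7.5 is used, put baseline and outcome on the same scale. Mean changes per arm can remain as description.

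State in section 7.1.2 which pre-randomization reading is the baseline and how it is measured. Report the SD of 12-week pressure, the SD of change and the baseline-to-12-week correlation, so that section 8.1 can be redone for the chosen analysis.

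The cost is one sentence for the model, short additions for the reporting and the baseline definition, and one degree of freedom. No new variable is needed.

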1.4 Expected results

We expect to estimate the participation rate and variance of the blood pressure. These estimates will be used in planning a future randomized controlled trial.

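### Section 8.3 leaves the pre-randomization weight, waist and hip values out of the 12-week comparison and does not say whether values or changes are compared

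*Combined protocol and SAP*

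**What the plan says.** Section 7.1.1 introduces its tertiary list with "Tertiary outcomes after 12 weeks will include". The anthropometric block of that list contains body weight, height and "Waist + hip circumference", all measured and continuous. Section 7.1.2 opens with "Before the participants are randomized following baseline data will be collected", and its table contains the same measures.

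The analysis is in the second paragraph of section 8.3: "Tertiary outcome measures will be analyzed as intention-to-treat using unpaired student t-test for continuous variables". No covariate is named and the analysed response is not defined. The preceding paragraph of 8.3 does refer to baseline and ends with "Results will be reported as mean difference of changes with 95 percent confidence intervals", but it concerns systolic blood pressure only.

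No other section fills the gap. Section 9.3 recognises that randomization may not balance the groups ("But given the limited sample-size we cannot be certain that this will be the case"), but the only remedy it discusses is stratified randomization, which it defers. On size, section 8.1 states "We will therefore only include 40 participants in this phase of the study".

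**The concern.** A person's weight or girth at 12 weeks is likely to be strongly related to the same measure before randomization. A comparison of 12-week values that ignores the baseline carries all the between-person variation into the standard error, and with 40 participants that is costly. The baseline value that would remove much of it is already collected.

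The second problem is that the response is undefined. An unpaired t-test can be run on 12-week values or on changes, and the two can differ several-fold in precision. The wording leans towards values, because changes are mentioned only for blood pressure, but it does not settle the matter. The choice is left to the analyst.

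At stake is the width of the confidence intervals for three outcomes that serve the part of objective 2 (section 3.2) on cardiovascular risk factors other than blood pressure. Type I error is not at risk.

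**Working it through.** The plan gives no precision or power figure for these outcomes, so there is none to reproduce. The check compares three analyses of the same data.

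**Inputs**
- Total N = 40 (section 8.1). Twenty per arm is an assumption: equal allocation is stated only for the future full-size trial.
- Two-sided 5% level. Section 8.3 gives 5 percent; two-sided is assumed.
- Correlation r between baseline and 12 weeks: not in the documents. Assumed values are 0.5, 0.8, 0.9 and 0.95.
- Equal SD at both times and in both arms, and no dropout (assumptions).
- For an example in kilograms, a weight SD of 15 kg (assumption).

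**Variance of the between-group difference, relative to a t-test on 12-week values**
- 12-week values: 1.
- Changes: 2(1 − r).
- ANCOVA: (1 − r²)(1 + 1/36). The last factor is the cost of estimating the covariate slope with 40 participants, about 2.8%.

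Loss of precision against ANCOVA is 1 − Var(ANCOVA)/Var(method). The CI width ratio, 12-week values to ANCOVA, is 2.0244/(2.0262 × √ANCOVA variance), using the t quantiles on 38 and 37 degrees of freedom.

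| r | Variance, changes | Variance, ANCOVA | Loss, 12-week values | Loss, changes | CI width ratio, 12-week values to ANCOVA |
|---|---|---|---|---|---|
| 0.5 | 1.0 | 0.75 × 1.0278 = 0.771 | 23% | 22.9% | 1.14 |
| 0.8 | 0.4 | 0.36 × 1.0278 = 0.370 | 63% | 7.5% | 1.64 |
| 0.9 | 0.2 | 0.19 × 1.0278 = 0.195 | 80% | 2.4% | 2.26 |
| 0.95 | 0.1 | 0.0975 × 1.0278 = 0.100 | 90% | −0.2% | 3.16 |

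The loss for 12-week values passes one half at r = √(1 − 0.5/1.0278) = 0.717. A simulation of 40,000 trials at each r gave losses of 22.9%, 63.3%, 80.3% and 90.0% for values, and 23.3%, 7.8%, 2.6% and −0.1% for changes.

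**Example: weight, SD 15 kg, 95% CI half-width**
- 12-week values: 2.0244 × 15 × √(2/20) = 9.60 kg at every r.
- Changes: 9.60 × √(2(1 − r)) = 9.60, 6.07, 4.29 and 3.04 kg.
- ANCOVA: 2.0262 × 15 × √(2/20) × √(ANCOVA variance) = 8.44, 5.85, 4.25 and 3.04 kg.

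**Chance imbalance.** The baseline difference between arms has a standard error of √(2/20) = 0.316 SD, or 4.7 kg at SD 15. A difference at least that large arises by chance in about one trial in three. ANCOVA allows for it; a t-test on 12-week values does not.

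**The case against.** The strongest reply is that this is a preference for efficiency and not an error. The t-test is valid, the trial is about feasibility, and section 1.4 names its planning outputs: "We expect to estimate the participation rate and variance of the blood pressure". Neither depends on weight, waist or hip, so no decision described in the plan would change. That is correct, and it limits the priority.

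The large losses also rest on an assumed r and on the reading that 12-week values are compared. If changes were intended, the loss at high r almost disappears, and high r is exactly where the loss for values looks dramatic. This stands as a caution: the two sets of losses must be read together. It does not remove the point, because the plan does not say which response is meant. One block of the tertiary table in section 7.1.1 is labelled as behaviour change, but that label does not extend to the anthropometric rows.

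The kilogram half-widths are a best case, since they assume complete follow-up and section 9.1 calls loss to follow-up the main threat to validity. Departures from 20 per arm or from full follow-up hardly alter the relative losses.

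Finally, waist and hip share one table row, so the plan does not say whether they are to be analysed separately. The wording of the fix has to settle that, but the case for adjustment is the same either way.

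**Conclusion.** The point holds. Weight, waist and hip are available before randomization, section 8.3 does not use those values, and it does not define the response. Under the natural reading, a comparison of 12-week values, the 95% confidence interval is 1.14 to 3.16 times as wide as with ANCOVA for r from 0.5 to 0.95. If changes are compared, the loss of precision is 23% at r = 0.5 and negligible at 0.95. ANCOVA is as precise as the better of the two, or very nearly so, at every r examined, so adopting it also removes the ambiguity. These figures assume 20 per arm, equal SDs and complete follow-up, and r is not in the documents. The change is worth considering but not critical, because the outcomes are tertiary and the trial is a feasibility study.

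**What to change.** Add to section 8.3:

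> Body weight, waist circumference and hip circumference at 12 weeks will each be analysed by ANCOVA with treatment group and the participant's own baseline value of that measure. The adjusted between-group difference will be reported with its 95% confidence interval.

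If a combined waist–hip measure is intended, name it and adjust it for its own baseline in the same way. Keep the unpaired t-test for continuous outcomes with no baseline value, such as the medication-adherence score, which is absent from the section 7.1.2 table. State also that height is recorded for description and is not tested; it is listed as a continuous tertiary outcome, so section 8.3 as written would test it.

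The cost is a change of wording. No new data are needed. Each model uses one degree of freedom, about a 2.8% increase in variance with 40 participants, which is already included in the figures above.

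### Section 8.3 has no method for ordered outcomes: self-rated health goes to an order-blind test, and physical activity has no assigned test

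*Combined protocol and SAP*

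**What the plan says.** Section 8.3 assigns tertiary outcomes to an unpaired t-test if continuous and to "either chi-squared test or fisher's exact test for categorical variables". Section 8.2 applies the same pair of rules to baseline characteristics. No rank test, trend test or ordinal model appears anywhere in the document.

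The variable tables use a third type. In the tertiary outcome table of section 7.1.1, physical activity reads "Physical activity Questionnaire Ordinal" and self-rated health reads "Two item questionnaire Categorical". In the baseline table of section 7.1.2, self-rated health is again a two-item questionnaire but is typed ordinal, and physical activity is typed ordinal. The number of levels is not given for either outcome.

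Section 8.3 promises a confidence interval for systolic blood pressure only. It does not say how baseline values enter the tertiary comparisons. On size, section 8.1 says: "We will therefore only include 40 participants in this phase of the study".

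**The concern.** The plan contradicts itself on self-rated health: the same measure is ordered in one table and unordered in the other, and the unordered label decides the test. A chi-squared or Fisher test on a two-by-k table gives the same p-value however the columns are arranged. It therefore spreads its sensitivity over every pattern of difference, including patterns that nobody expects, and it gives a p-value without a direction or a summary effect.

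For physical activity the defect is silence. It is one of the three behaviours that the intervention targets (section 3.2). With no rule, the analyst can pick a t-test on scores, a chi-squared test or a rank test after seeing the data.

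Both outcomes are also recorded before randomization, and the tertiary analysis makes no stated use of those values.

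**Working it through.** **What the plan computes.** No power is stated for any ordered outcome, so there is no figure to reproduce. The only derived sample size, 596 in section 8.1, concerns systolic blood pressure in a future trial and has no bearing here.

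**Which rule applies**

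| Outcome | Type at baseline (7.1.2) | Type at 12 weeks (7.1.1) | Test under 8.3 |
|---|---|---|---|
| Self-rated health | Ordinal | Categorical | Chi-squared or Fisher |
| Physical activity | Ordinal | Ordinal | None assigned |

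**Inputs from the plan.** Total size is 40 (section 8.1). The test level is 5%: "A significance level of 5 percent will be considered statistically significant" (section 8.3).

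**Assumptions.** 20 per arm with no losses, two-sided testing, 3 to 5 levels, and a proportional-odds shift with odds ratio (OR) 2, 3, 5 or 8. The documents fix none of these.

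**The shift.** If the cumulative probability in the control arm is F, the cumulative odds F/(1 − F) are divided by the OR. With five even levels and OR 3:
- control cumulative odds: 0.25, 0.667, 1.5, 4
- divided by 3: 0.083, 0.222, 0.5, 1.333
- cumulative probabilities: 0.077, 0.182, 0.333, 0.571
- level probabilities: 0.077, 0.105, 0.151, 0.238, 0.429, against 0.2 in each level for control

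**Simulated power.** 2,500 trials per row; relative loss = 1 − (power of chi-squared or Fisher) / (power of the tie-corrected Wilcoxon test), taken before rounding.

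| Even levels | OR | Wilcoxon | Chi-squared | Fisher | Loss, chi-squared / Fisher |
|---|---|---|---|---|---|
| 3 | 2 | 0.214 | 0.171 | 0.155 | 20% / 27% |
| 3 | 3 | 0.437 | 0.337 | 0.318 | 23% / 27% |
| 3 | 5 | 0.732 | 0.628 | 0.607 | 14% / 17% |
| 3 | 8 | 0.899 | 0.829 | 0.812 | 8% / 10% |
| 4 | 2 | 0.224 | 0.137 | 0.136 | 39% / 39% |
| 4 | 3 | 0.454 | 0.308 | 0.310 | 32% / 32% |
| 4 | 5 | 0.763 | 0.587 | 0.595 | 23% / 22% |
| 4 | 8 | 0.925 | 0.804 | 0.811 | 13% / 12% |
| 5 | 2 | 0.227 | 0.125 | 0.128 | 45% / 44% |
| 5 | 3 | 0.484 | 0.276 | 0.290 | 43% / 40% |
| 5 | 5 | 0.785 | 0.552 | 0.578 | 30% / 26% |
| 5 | 8 | 0.936 | 0.781 | 0.805 | 17% / 14% |

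The simulation error is at most √(0.5 × 0.5 / 2500) = 0.01. With bell-shaped or skewed five-level scales the losses run from 14% to 52%. At OR 1 all three tests reject in about 4-5% of trials on the even, bell-shaped and skewed scales, so an inflated type I error does not explain the gain.

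**Cross-check without simulation.** A directional test puts the signal on 1 degree of freedom, and the chi-squared test spreads the same noncentrality over k − 1.
- Where the 1-df test has 50% power, the (k − 1)-df test has 40.1%, 34.5% and 30.8% for k = 3, 4 and 5. For k = 5 the loss is 1 − 0.308/0.5 = 38%; for k = 3 and 4 it is 20% and 31%.
- Where the 1-df test has 80% power, the figures are 70.9%, 64.5% and 59.5%, so the losses are 11%, 19% and 26%.

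**If physical activity were given a t-test on its scores.** Power stays within about 6% of the Wilcoxon test on the even, bell-shaped and skewed scales. The power loss therefore arises only if chi-squared or Fisher is chosen.

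**The case against.** The strongest reply is that little depends on this. The outcomes are tertiary, the main objective is feasibility, and section 8.1 itself says that a larger trial would be needed to expect an effect. Section 1.4 names the participation rate and the blood-pressure variance as the estimates to carry forward, and neither depends on these tests. That stands, and it limits the severity.

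It is also fair that proportional-odds data favour a rank test by construction, and that the size of the loss is a product of assumptions. Four stronger readings are tempting, and the documents do not support them.

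- **A fixed loss of a third or more.** This holds for roughly four or more levels with a modest one-directional shift. It fails for three levels and for large effects, and the plan gives no level counts for these two outcomes.
- **Physical activity is sent to chi-squared.** It is not. It is typed ordinal, and section 8.3 is silent on that type.
- **Smoking has the same problem.** Its levels are "Daily; weekly; Rarely; Former; Never smoked". A smoker who quits can only become a former smoker, so the change is not a shift along the whole scale. With an assumed smoking distribution and 10 to 20 percentage points moving from daily to former, power was 0.07-0.14 for Wilcoxon, 0.07-0.25 for chi-squared and 0.10-0.33 for Fisher. A baseline-adjusted ordinal model is also prone to separation, because never-smokers stay never-smokers. The categorical typing is defensible.
- **Satisfaction is affected.** It is recorded on a "Five level Likert Scale", but it rates the intervention itself, and no comparison between arms is planned.

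**Conclusion.** The point holds in a limited form. Section 8.3 lacks a method for ordered outcomes, the two tables contradict each other on self-rated health, and physical activity has no test. These three facts are on the page and need no assumption.

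The cost in power is conditional: roughly 10-50% of rank-test power, given 20 per arm, a proportional-odds shift and 3 to 5 levels. It is smaller with fewer levels or larger effects. For physical activity it arises only if chi-squared or Fisher is the test chosen. The lack of a direction and an effect estimate for self-rated health does not depend on those assumptions.

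Severity is minor. No feasibility or blood-pressure conclusion changes.

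**What to change.** In section 7.1.1, type self-rated health as ordinal, to match section 7.1.2. State the number of levels for self-rated health and physical activity, and whether the two self-rated health items are analysed singly or combined.

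In section 8.3, add: *Physical activity and self-rated health at 12 weeks are compared between arms with a proportional-odds model adjusted for the baseline level, reported as a common odds ratio with 95% confidence interval. If the model does not converge, a Wilcoxon rank-sum test is used.* Keep chi-squared or Fisher for smoking and other categorical outcomes. Confirm that physical activity uses the same questionnaire at both visits, because the baseline adjustment assumes it.

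The cost is a few lines of SAP text and minor analysis work, with no new data. The downsides are the proportional-odds assumption, which 40 participants can hardly test, and possible non-convergence at that size. The rank-sum fallback covers non-convergence but gives up the baseline adjustment and the odds ratio.
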